T_{max} observed time to reach peak plasma concentration

TK tyrosine kinase

ULN upper limit of normal

VEGFR2 vascular endothelial growth factor receptor 2

STUDY SYNOPSIS

Protocol number:	Study drug: Tesevatinib (KD019)
KD019-211	

Title of the study:

A Double-blind Randomized Parallel Group Study of the Efficacy and Safety of Tesevatinib in Subjects with Autosomal Dominant Polycystic Kidney Disease

Number of subjects (total and for each treatment arm):

Approximately 160 subjects will be screened in order to enroll 100 subjects (50 subjects randomized to tesevatinib, 50 subjects randomized to placebo) of which at least 80 subjects (40 per group) are anticipated to complete all study procedures.

Investigator(s):

Multicenter study in the United States. Coordinating Principal Investigator –

Site(s): Approximately 25-30 sites in the United States

Study period (planned): Clinical phase: 2b
June 2017 to June 2020

Objectives:

Primary:

To evaluate the change from baseline in height-adjusted total kidney volume (htTKV) as measured by magnetic resonance imaging (MRI) at Months 12, 18, 24, and 30 days post-dose in patients with autosomal dominant polycystic kidney disease (ADPKD) treated with tesevatinib or placebo.

Secondary:

To evaluate the safety and tolerability of tesevatinib 50 mg once daily (QD) in patients with ADPKD.

To evaluate the change in eGFR using the MDRD-4 formula at the Month 12, 18, 24, and 30 days post-dose time points.

Rationale:

In nonclinical studies, tesevatinib selectively inhibited key kinases and validated targets in animal models of polycystic kidney disease (PKD). This Phase 2b, double-blind, placebo-controlled study in subjects with ADPKD will provide initial evidence of the treatment effect of tesevatinib in ADPKD subjects and allow for a better understanding of tesevatinib's safety profile in this patient population.

Investigational product, dose, and mode of administration:

Tesevatinib (KD019) 50 mg or matched placebo tablets will be administered orally QD.

Methodology:

This is a multicenter, double-blind, randomized, parallel group study of tesevatinib tablet formulation administered to male and female subjects with ADPKD, 18 to 60 years of age and with an estimated glomerular filtration rate (eGFR) \geq 30 mL/min/1.73 m² and < 80 mL/min/1.73 m².

Subjects will be screened up to 28 days before initiation of treatment with tesevatinib or placebo (certain screening assessments may be conducted up to 42 days prior to dosing). Screening assessments will include medical and PKD history, physical examination, vital signs, electrocardiograms (ECGs), clinical laboratory evaluation (including hematology, serum chemistry, coagulation, thyroid stimulating hormone, urinalysis, and pregnancy), ocular examination, echocardiogram, and MRI. Calculation of htTKV at screening for eligibility determination may be performed by a local radiologist.

Starting on Day 1, subjects will receive 50 mg QD of tesevatinib or placebo for up to 24 months. During the Early Treatment Period (Days 1 to 28), subjects will report to the study site on Days 1, 14, and 28; subjects will be followed every 28 days from Months 2 to 12 and every other month from Months 12 to 24. Safety assessments will be performed at regular intervals throughout the study and will include physical examinations, vital signs, ECGs, clinical laboratory evaluations, ocular examination and echocardiograms. Magnetic resonance imaging to determine the change from baseline in htTKV will be performed at Months 12, 18, and 24. Entry into the study will be based on local MRI readings, but central MRI readings and htTKV calculation will be performed at baseline and during the study.

All subjects will undergo an end-of-study evaluation approximately 30 days after the last dose of study drug.

Inclusion and exclusion criteria:

Inclusion criteria:

Subjects will be included in the study if they meet all of the following inclusion criteria:

- 1. Confirmed diagnosis of ADPKD based on Ravine's criteria. Subjects < 30 years of age must have at least 2 cysts (unilateral or bilateral) while subjects ≥ 30 years of age must have at least 2 cysts in each kidney (ie, total ≥ 4 cysts).
- 2. Cysts must be at least 1 cm in size to be considered.
- 3. At least 18 years old and no more than 60 years old at the time of consent.
- 4. eGFR ≥ 25 mL/min/1.73 m² and ≤ 90mL/min/1.73 m², using the Modification of Diet in Renal Disease-4 variable formula.
- 5. htTKV must meet the following requirements (htTKV is calculated using total kidney volume obtained from MRI divided by height in meters):
 - >500 mL for subjects 18-35 year of age
 - >750 mL for subjects 36-49 years of age
 - >900 mL for subjects 50-60 years of age
- 6. Subject has the following laboratory values:
 - Platelets > lower limit of normal (LLN)

- Hemoglobin > 9 g/dL
- Total bilirubin $\leq 1.5 \text{ mg/dL}$
- Aspartate aminotransferase $< 2.5 \times$ upper limit of normal (ULN)
- Alanine aminotransferase $< 2.5 \times ULN$
- Prothrombin time/partial thromboplastin time $\leq 1.5 \times ULN$
- International normalized ratio (INR) \leq 1.5, except those subjects taking warfarin who must have INR \leq 3
- Albumin \geq LLN
- Amylase $\leq 1.5 \text{ x ULN}$
- Lipase < 1.5 x ULN
- Serum potassium within normal limits
- Serum magnesium within normal limits
- 7. Female subjects of childbearing potential must have a negative pregnancy test at screening. Females of childbearing potential are defined as sexually mature women without prior hysterectomy, bilateral tubal ligation, or who have had any evidence of menses in the past 12 months. However, women who have been amenorrheic for 12 or more months are still considered to be of childbearing potential if the amenorrhea is possibly due to prior chemotherapy, anti-estrogens, or ovarian suppression.
 - Women of childbearing potential must have a negative urine pregnancy test (positive urine tests are to be confirmed by serum test) documented within the 24-hour period prior to the first dose of study drug.
 - Sexually active women of childbearing potential enrolled in the study must agree to use 2 forms of accepted methods of contraception during the course of the study and for 6 months after their last dose of study drug. Effective birth control includes (a) intrauterine device **plus** 1 barrier method; (b) on stable doses of hormonal contraception for at least 3 months (eg, oral, injectable, implant, and transdermal) **plus** 1 barrier method; or (c) 2 barrier methods. Effective barrier methods are male or female condoms, diaphragms, and spermicides (creams or gels that contain a chemical to kill sperm); or (d) a vasectomized partner.
- 8. For male subjects who are sexually active and are partners of premenopausal women: agreement to use 2 forms of contraception as in criterion 7 above during the treatment period and for at least 6 months after the last dose of study drug, unless the male subject had a vasectomy.
- 9. Capable of understanding and complying with the protocol and has signed the informed consent form.

Exclusion criteria:

Subjects meeting any of the following criteria will be excluded from participation:

- 1. Previous partial or total nephrectomy or a kidney transplant.
- 2. Tuberous sclerosis, Hippel-Lindau disease, or acquired cystic disease.

- 3. Congenital absence of 1 kidney and/or need for dialysis or transplantation in the foreseeable future.
- 4. Moderate hematuria. Subjects with microhematuria may be enrolled, unless microhematuria is suspected to be due to infection or recent cyst rupture. If hematuria is due to cyst rupture, the subject may be rescreened after discussion with the Medical Monitor.
- 5. Uncontrolled hypertension (systolic blood pressure > 160 mmHg; diastolic blood pressure > 100 mmHg) while receiving antihypertensive therapy.
- 6. Uncontrolled diabetes mellitus (glycated hemoglobin > 8%).
- 7. Presence of renal or hepatic calculi (stones) causing symptoms.
- 8. Received any investigational therapy within 30 days prior to initiation of therapy (Day 1).
- 9. Received tolvaptan within 30 days prior to initiation of therapy (Day 1).
- 10. Received active treatment (within 4 weeks of initiation of therapy [Day 1]) for urinary tract infection.
- 11. History of pancreatitis or known risk factors for pancreatitis.
- 12. Subject meets any of the following cardiac criteria:
 - Mean QTc interval corrected for heart rate using Fridericia's formula (QTcF) of > 450 msec.
 - History of torsade de pointes, ventricular tachycardia or fibrillation, pathologic sinus bradycardia (< 50 beats per minute), heart block (excluding first-degree block, being PR interval prolongation only), congenital long QT syndrome or new ST segment elevation or depression or new Q wave on ECG. Inclusion of subjects with a history of atrial arrhythmias should be discussed with the Medical Monitor.
 - Family history of congenital long QT syndrome or unexplained cardiac death.
 - History of ventricular rhythm disturbances.
 - Symptomatic heart failure (per New York Heart Association guidelines), unstable angina, myocardial infarction, or cerebrovascular accident within 6 months prior to study entry.
 - Has a cardiac pacemaker.
 - History of pericardial effusion or presence of pericardial effusion on screening echocardiogram
- 13. Subject is taking any medication known to inhibit the cytochrome P450 (CYP)3A4 isozyme or any drugs that are CYP3A4 inducers, or any drugs associated with torsade de pointes or known to prolong the QTcF interval, including anti-arrhythmic medications within 2 weeks prior to screening. A stable regimen (≥ 4 weeks) of antidepressants of the selective serotonin reuptake inhibitor (SSRI) class is allowed (common SSRIs include escitalopram oxalate, citalopram, fluvoxamine, paroxetine, sertraline, and fluoxetine).
- 14. Uncontrolled intercurrent illness that would limit compliance with study requirements including, but not limited to ongoing or active infections or psychiatric illness.
- 15. Subject is pregnant, plans to become pregnant, or nursing.

16. Known to be positive for the human immunodeficiency virus or hepatitis B or C, as indicated by a positive test at screening.

- 17. Known to be immunocompromised.
- 18. Documented presence of renal vascular disease resulting in uncontrolled hypertension.
- 19. Has previously received an epithelial growth factor receptor (EGFR) inhibitor (including, but not limited to, erlotinib, gefitinib, osimertinib, afatinib, cetuximab, panitumumab, or an investigational agent).
- 20. Allergy or hypersensitivity to components of either tesevatinib, matched placebo, or their formulations.
- 21. Aphakic due to previous cataract surgery or congenital abnormality.

Note: The sponsor has the option to exclude a subject from enrollment, if, based upon the subject's medical history or screening results, it is felt that a subject's safety may be at risk and/or if the safety data may confound the study results.

Maximum duration of subject involvement in the study:

The planned duration of the screening period is no more than 28 days prior to dosing (42 days for MRI and ocular assessments). The planned duration of treatment period is approximately 730 days (or 24 months). The follow-up period will be 30 days from the last dose of study drug.

Endpoints and statistical analysis:

Study data will be summarized for disposition, demographic and baseline characteristics, efficacy, and safety parameters. Unless otherwise noted, study data will be summarized by treatment group. Categorical data will be summarized by frequency distributions (number and percentages of subjects) and continuous data will be summarized by descriptive statistics (mean, standard deviation, median, minimum, and maximum). All data will be presented in subject listings.

Efficacy analyses will be based on the Efficacy Population, defined as all randomized subjects who have completed 12 months of tesevatinib or placebo treatment and have a centrally read MRI at baseline and after 12 months of treatment. The primary efficacy endpoint will be the change from baseline in htTKV at Month 12. An analysis of covariance model including treatment group as a factor and the baseline htTKV as a covariate will be used for efficacy analyses. The Type I error rate will be set at an alpha level of 0.05. Additional efficacy endpoints include change from baseline in htTKV at Months 18 and 24.

Safety analyses will be based on the modified Intent-To-Treat Population, defined as all randomized subjects who received at least 1 dose of study drug. Treatment-emergent adverse events (AEs) will be summarized using Medical Dictionary for Regulatory Activities (Version 19.0 or higher) system organ class and preferred term and presented by treatment group. Safety endpoints will include AEs and clinical laboratory evaluations (including serum creatinine, cystatin C, and calculated eGFR).

Based on the results presented in Caroli, et.al.¹ it is anticipated that the mean change from baseline in htTKV at 12 months will be 83.6 (± 90.0) mL in the placebo group. Assuming the mean change from baseline in htTKV at 12 months is 26.4 mL for the tesevatinib group, 40 subjects per group would yield approximately 80% power to detect a difference between

treatment groups based on a 2-sided t-test with a Type I error rate of 0.05. Ten additional subjects per group will be added (ie, for a total of 50 subjects per group) to adjust for drop-outs and differences in analysis methodologies (eg, the htTKV data will be log-transformed).

STUDY SCHEDULE

Table 2: Schedule of Assessments

			Early Treatment Period			End of Study ^c
Assessments	Screening ^a (-28 Days)	Day 1	Day 14 (± 1 Day)	Day 28 (± 1 Day)	Every 28 Days ^b Beginning at Month 2 (± 1 or ±3 Days)	30 Days from Last Dose (± 3 Days)
Informed consent	>					
Medical and PKD history (include genotype, if available)	*					
Physical examination ^d (including weight)	~	~	~	~	~	~
Vital signs ^e	~	~	~	~	~	~
Supine 12-lead ECG ^f	~	~	~	~	~	~
Clinical laboratory tests ^g	~	~	~	~	~	~
Ocular evaluation ^h	>				•	>
Echocardiogram ⁱ	>			~	~	~
Pregnancy test ^j	>	~		~	~	~
MRI ^k	•				(every 6 months beginning at Month 12)	•
Randomization		~				
Study drug/placebo dispensed		~	~	*	~	>
Record adverse events	>	~	~	~	~	~
Record concomitant medication	>	~	~	*	•	>
Drug compliance/collection ¹		~	~	~	~	~

Abbreviations: ECG, electrocardiogram; MRI, magnetic resonance imaging; PKD, polycystic kidney disease; QTc(F), QT interval corrected for heart rate using Fridericia's formula; TSH, thyroid stimulating hormone

- a. Screening evaluations may be combined with Day 1 pre-treatment laboratory evaluations if both are done within 4 days before first dose of study drug. Screening MRI and ocular assessments may be performed up to 6 weeks prior to Day 1.
- b Follow-up treatment period visits to be performed monthly (every 28 ± 1 day). For those subjects continuing on study beyond 12 months, visits will occur every 2 months ± 3 days between Months 12 and 24.
- c. The End-of-study visit is to be performed 30 days (± 3 days) after last dose of study drug.
- d. A complete physical examination is to be done at the Screening and End-of-study visits. Height will only be measured at Screening. Symptom-driven physical examinations will be performed on Days 1, 14, 28, every 28 days from Months 2 to 12, and every 2 months from Months 12 to 24. See Section 7.5.1 for a description of the body systems and evaluations to be performed at each visit (eg, cardiac tamponade, ocular toxicity and xerostomia assessments).
- e. Vital sign measurements will include sitting blood pressure, heart rate, respiratory rate, and oral or tympanic temperature. On Day 1, measurements should be performed predose and 1 and 4 hours postdose. See Section 7.5.2 for details on vital signs measurement.
- f. Supine 12-Lead ECGs will be performed at Screening, predose, 1, 4, and 8 hours postdose on Days 1 and 14; predose on Days 28 and Months 2 to 12, at each visit on Months 12 to 24; and at the End-of-study visit. Supine ECGs should be repeated 3 times consecutively within 30 minutes (with an interval of at least 1-2 minutes between ECGs). If QTc(F) is prolonged to > 60 msec above baseline at any evaluation or to the level of ≥ 480 msec based on local ECG read, refer to Section 6.7.1.2 for a description of the procedures to be followed.
- g. Clinical laboratory tests will include hematology, serum chemistry, coagulation, TSH, and urinalysis (see Section 7.5.6 for a complete list of assessments). Thyroid stimulating hormone levels will be evaluated at Screening and then every 2 months. Serology testing will be done at Screening only.
- h. Ocular evaluations are to be performed at Screening and at Months 3, 6, 9, 12, 18, and 24, and at the End-of-study visit (if applicable). The following assessments will be performed: evaluation of best corrected visual acuity, fundoscopic exam with non-dilated pupils, slit lamp photography of the iris, non-mydriatic photography of retina within the arcade, and optical coherence tomography of the optic nerve head and macula. Note: if a subject has had ocular evaluations within 3 months of the End-of-study visit, there is no need to repeat ocular evaluations at the End-of-study visit.
- i. Echocardiograms are to be obtained at Screening, on Day 28, at Months 3, 6, 12, 18, and 24, and at the End-of-study visit (if applicable). Echocardiograms should include measurement of ejection fraction and assessment for pericardial effusion and valvular abnormalities. Note: If a subject has had an echocardiogram within 3 months of the End-of-study visit, there is no need to obtain an echocardiogram at the End-of-study visit. If pericardial effusion is diagnosed via echocardiogram, the subject should be rechecked within 1–3 months to monitor for progression.
- j. Pregnancy testing in women of childbearing potential will be performed using urine samples. Subjects must have a negative urine pregnancy test documented within the 24-hour period prior to the first dose of study drug. Pregnancy tests are to be performed at Screening, predose on Day 1, Day 28, Month 3, every 3 months through Month 12, at every visit between Months 12 and 24, and at the End-of-study visit only. Positive urine samples will be confirmed via serum testing.
- k. Screening MRI will be performed after informed consent form has been signed and prior to other screening assessments. Magnetic resonance imaging will be performed at Month 12, 18, and 24, and at the End-of-study visit
- 1. Subject diaries will be dispensed on Day 1 and reviewed/collected at each visit.

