6.7. Warnings, Precautions, and Management

Adverse events that have been associated with tesevatinib include the following: diarrhea, skin rash, QTcF prolongation, hepatotoxicity, and pulmonary toxicity. Study drug may be held for up to 28 days at the discretion of the Investigator (unless otherwise specified below), except during the first 28 days of dosing (Early Treatment Period).

Diarrhea

Diarrhea should be managed according to accepted practice (eg, with loperamide). Subjects with severe diarrhea who are unresponsive to loperamide or who become dehydrated may require interruption of study drug until resolution to ≤ mild in intensity. If subjects are in the monthly treatment period, drug may be held for up to 28 days. If severe diarrhea occurs during the 28-day Early Treatment Period, subjects must be discontinued from the study. In the event of severe or persistent diarrhea, nausea, anorexia, or vomiting associated with dehydration, study drug should be discontinued, and appropriate measures should be taken to rehydrate the subject intensively via intravenous administrations. Subjects should be advised to contact the investigator immediately if they develop significant diarrhea; should this occur, an electrolyte panel, including magnesium and potassium, and ECG should be performed.

Skin Rash

Skin rash should be managed according to locally accepted clinical recommendations. Study drug may be held up to 28 days at the discretion of the investigator and after discussion with the Medical Monitor. The following guidelines may be considered.

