7. STUDY PROCEDURES

7.1. Study Schedule

The schedule of assessments for this study is provided in Table 2.

All screening assessments are to be performed within 28 days prior to the first dose of study drug, unless otherwise specified. Study eligibility will be based on satisfying all of the study inclusion and exclusion criteria. Day 1 is defined as the date the subject takes the first dose of study drug.

A screen failure is a subject who has given informed consent and failed to meet the inclusion and/or meet at least 1 of the exclusion criteria and has not been randomized or administered investigational product(s) as defined by the protocol.

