3.13.5 Echocardiogram

The results of the echocardiogram (ie, normal, abnormal, and abnormal clinically significant) will be summarized by treatment group for each valve (ie, aortic, mitral, tricuspid, and pulmonic) at each scheduled assessment timepoint.

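### The End-of-study echocardiogram and ocular waivers in Protocol Table 2 can be met by the pre-treatment screening examination, so an early stopper can leave with no post-dose echocardiogram or footnote-h ocular evaluation

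*Protocol*

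**What the plan says.** Table 2 of the Protocol schedules an echocardiogram and an ocular evaluation at the End-of-study visit, which falls 30 days (± 3) after the last dose (footnote c). Two footnotes then waive them:

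- Footnote i, echocardiogram: "If a subject has had an echocardiogram within 3 months of the End-of-study visit, there is no need to obtain an echocardiogram" at that visit.
- Footnote h, ocular: "if a subject has had ocular evaluations within 3 months of the End-of-study visit, there is no need to repeat ocular evaluations" at that visit.

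The examinations that could trigger the waiver are set in the same footnotes. For echocardiograms: "Echocardiograms are to be obtained at Screening, on Day 28, at Months 3, 6, 12, 18, and 24". For ocular evaluations: "Ocular evaluations are to be performed at Screening and at Months 3, 6, 9, 12, 18, and 24". Screening therefore counts as one of the scheduled examinations.

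Protocol Section 7.1 gives the screening window: "All screening assessments are to be performed within 28 days prior to the first dose of study drug, unless otherwise specified". Footnote a of Table 2 specifies otherwise for two assessments: "Screening MRI and ocular assessments may be performed up to 6 weeks prior to Day 1".

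For withdrawals, Protocol Section 4.3 asks sites to make every effort to complete the End-of-study procedures. It points to Table 2 for what these are, so the waiver applies there too.

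**The concern.** A waiver of this kind spares a subject a second examination soon after a recent on-treatment one. As worded, it looks back a fixed 3 months from the End-of-study visit and does not ask whether the earlier examination was made on drug. For a subject who stops early, the look-back reaches past Day 1 to screening.

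That matters most for the echocardiogram. Protocol Section 6.7 names pericardial effusion as a risk seen in oncology studies, with one trace effusion in an ADPKD subject at 50 mg daily, the dose tested here. Exclusion criterion 12 bars anyone with a history of effusion or with effusion on the screening echocardiogram. The screening echocardiogram is therefore free of effusion by design: it is a baseline and cannot show a drug effect. Safety and tolerability at 50 mg is a secondary objective (Section 2.2). Early stopping is a foreseen path: "If severe diarrhea occurs during the 28-day Early Treatment Period, subjects must be discontinued from the study".

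**Working it through.** The plan states no figure for this gap, so there is none to reproduce. The check is date arithmetic.

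**Inputs**

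- s = days by which the screening examination precedes Day 1: up to 28 for echocardiogram (Section 7.1), up to 42 for ocular (Table 2, footnote a).
- d = study day of last dose. Day 1 is the first dose and there is no Day 0 (SAP 3.2.2).
- 30 + w = days from last dose to the End-of-study visit, with w from −3 to +3 (Table 2, footnote c).
- L = length of 3 months in days. The Protocol does not define it. I take 91 and show 89 to 92.

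**Formula**

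Gap from screening examination to End-of-study visit = s + (d − 1) + (30 + w). The waiver is met when the gap is no more than L, that is, when d ≤ L − s − (30 + w) + 1.

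**Echocardiogram**

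The longest gap for a stop before the Day 28 echocardiogram has s = 28, d = 27, w = +3:

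28 + 26 + 33 = 87 days.

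This is below even the shortest reading of 3 months (89 days). If the last dose is on Day 28 itself and that day's echocardiogram is missed, the gap is 28 + 27 + 33 = 88 days, still below 89. So the waiver is met for every such subject, whatever the screening date or visit window.

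**Ocular evaluation**

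The first on-treatment evaluation is at Month 3. The latest last-dose day on which the screening evaluation still meets the waiver is:

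| Screened before Day 1 | L = 91, visit at 30 days | Shortest (L = 89, visit at 33) | Longest (L = 92, visit at 27) |
|---|---|---|---|
| 42 days | 91 − 42 − 30 + 1 = Day 20 | Day 15 | Day 24 |
| 28 days | 91 − 28 − 30 + 1 = Day 34 | Day 29 | Day 38 |
| 1 day | 91 − 1 − 30 + 1 = Day 61 | Day 56 | Day 65 |

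All of these fall before Month 3, which is Day 84 if months are counted as 3 × 28 days. A subject stopping by the day shown would have no on-treatment ocular evaluation on file. Unlike the echocardiogram, the ocular waiver is not always met in the Early Treatment Period. With screening 42 days before Day 1 and a last dose on Day 28, the gap is 42 + 27 + 30 = 99 days (96 to 102 across the window), so the End-of-study evaluation is still due.

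**Does another section close the gap?**

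- Section 4.3 refers back to Table 2 and so to the waiver.
- The repeat echocardiogram at 1 to 3 months (footnote i and Section 6.7) starts only once an effusion has been found.
- Footnote d and Section 7.5.1 provide physical examinations, which are weighed below.

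**The case against.** Four points on the other side have force.

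1. Such a subject is not unexamined. Footnote d requires a complete physical examination at End-of-study and symptom-driven ones at earlier visits. The limited examination in Section 7.5.1 covers pupils, ophthalmoscopy and eye movements, and Section 6.7 asks for signs of tamponade. This stands and limits the claim: what can be missing is the echocardiogram and the footnote-h ocular evaluation (acuity, slit-lamp and retinal photography, optical coherence tomography). The physical examination does not replace them, because an asymptomatic effusion would not be expected to show on it.

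2. The waiver is permissive. A site may still do the examinations, and a clinically indicated one is not blocked. This stands: the gap is possible, not certain.

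3. The Protocol does not say that the Day 28 visit lapses when dosing stops. For a last dose on Day 1, the nominal End-of-study visit is on Day 31, after Day 28. This stands in part. Section 4.3 does not settle the matter, and a subject discontinued from the study for severe diarrhea has no evident reason to attend on Day 28.

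4. No primary endpoint, alpha or power is affected. This is correct.

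A reader might also infer more than the documents support:

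- **A larger loss in the active arm.** No early-stop rate at 50 mg is given, the rash withdrawals described were at 150 mg, and Section 1.2 reports 50 mg as well tolerated.
- **Early toxicity generally forces subjects off drug because holds are barred in the first 28 days.** The general hold in Section 6.7 is barred then, but the specific provisions for rash, QTcF, amylase, pulmonary symptoms and liver tests carry no such exclusion. Among these toxicities, mandatory early discontinuation is explicit only for severe diarrhea.
- **The waiver is a defect throughout the 24 months.** For later stops it is mostly met by a recent on-treatment examination, which is its evident purpose.
- **The echocardiogram summary in SAP 3.13.5 needs changing.** It tabulates results by valve "at each scheduled assessment timepoint". Completers will mostly lack an End-of-study value because their Month 24 echocardiogram is recent, which is a reasonable saving. A different summary of valve results would not show effusion anyway.

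**Conclusion.** The point holds as a drafting gap in footnotes h and i. Followed as written, they let a screening echocardiogram stand in for the End-of-study one for every subject who stops before the Day 28 echocardiogram. This does not depend on how 3 months is read between 89 and 92 days. They do the same for the ocular evaluation up to a last-dose day that depends on the screening date: about Day 20, 34 or 61 under the 91-day and 30-day assumptions.

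The result rests on the subject not attending a Day 28 visit after stopping (for the echocardiogram) and on the site using the waiver. The number affected cannot be estimated, because the documents give no early-stop rate. It is probably small in a trial of 100 subjects. The consequence is confined to safety ascertainment: missing post-dose information on a named risk. Nothing here shows bias between arms or any effect on the efficacy analysis.

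**What to change.** In footnotes h and i of Table 2, state that only an evaluation performed after the first dose of study drug satisfies the 3-month waiver. Section 4.3 then needs no edit, because it already refers to Table 2. Defining 3 months in days in the same footnotes would remove the remaining ambiguity.

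The cost is one clause in each footnote. A few early stoppers will have the End-of-study echocardiogram and ocular evaluation that Table 2 already schedules. The waiver still applies to anyone with a recent on-treatment examination, and no dosing or stopping rule or SAP section changes.
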